11.4.5.1 Bleeding Events

Bleeding events will be classified into the following categories and summarized by treatment group, and analyzed in the same way as the primary endpoint.

- 1) Major bleeding
- 2) Major bleeding and clinically relevant non-major bleeding
- 3) Clinically relevant non-major bleeding
- 4) Minor bleeding

****** Subjects withdrawn from study participation

5) All bleeding events

11.4.5.2 Adverse Events

Incidences of adverse events will be calculated by treatment group. Frequencies of adverse events will also be tabulated by event and by severity. Adverse drug reactions will be analyzed in the same way.

In tabulation by System Organ Class or Preferred Term, if multiple adverse events with the same System Organ Class or Preferred Term occur in the same subject, these will be counted as a single event. System Organ Classes will be displayed in the internationally agreed order, and Preferred Terms will be displayed in code order. In this study, adverse events that occur after the initiation of study treatment (treatment emergent adverse events [TEAEs]) will be tabulated.

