6.13 Adverse Events

If an adverse event occurs between the initiation of study treatment and the examination at completion of study treatment or the examination at discontinuation, †††† a survey will be performed according to "9.4 Adverse Event Information to Be Reported" and the information will be entered on the case report form.

During study drug interruption and after study drug discontinuation, a survey to find whether any serious adverse events have occurred will be performed at least every 8 weeks, and if they have, a survey will be performed according to "9.4 Adverse Event Information to Be Reported" and the information will be entered on the case report form. Occurrence of any serious adverse events will be monitored until the final follow-up examination and will be reported in accordance with the Section "9.6.2 Action When a Serious Adverse Event Occurs."

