11.4.2.1.2 Secondary Analysis

The cumulative incidence of events will be estimated for each treatment group using the Kaplan-Meier method. Sensitivity analysis of the events that occur during the "on-treatment" period** in the mITT analysis set and PPS will be performed.

**: "On-treatment" period is defined as the study treatment period and up to 3 days after the last dose (approximately five times the half-life [T_{1/2}] of DU-176 corresponds to 3 days). If the subject resumes study drug, the subject is considered at risk again. However, in analysis, a subject who has received the study drug up to the examination at completion of study treatment will not be considered at risk after the day of the examination at completion of study treatment, and events that occur on or after the day of the examination at completion of study treatment will not be included in analysis. For subjects who do not experience an event while at risk, the time to onset of the initial event will be censored at 3 days after the final dose, the day of the examination at completion of study treatment, the examination at discontinuation (for subjects withdrawn from study participation), the day of the subject's last assessment, or death, whichever comes first.

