11.4.5 Safety Analysis

Unless otherwise stated, the safety analysis set will be used for safety analysis. The analysis period will be from the initiation of study treatment to the examination at completion of study treatment or the examination at discontinuation******. Serious adverse events observed during the period from the examination at completion of study treatment to the final follow-up examination and data obtained at the final follow-up examination will be tabulated separately, as necessary. Adverse events will be coded using the International Council for Harmonisation of Technical Requirements for Pharmaceuticals for Human Use (ICH) Medical Dictionary for Regulatory Activities (MedDRA), and system organ classes will be tabulated using MedDRA System Organ Classes, and adverse event terms will be tabulated using Preferred Terms.

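### The adverse event tables run past last dose into follow-up that does not ask about non-serious, non-bleeding events, and no exposure adjustment is stated

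*Combined protocol and SAP*

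**What the plan says.** - **Definition.** Section 11.4.5.2: "adverse events that occur after the initiation of study treatment (treatment emergent adverse events [TEAEs]) will be tabulated". The sentence gives a start and makes no reference to last dose. Incidences are to be calculated by treatment group, and adverse drug reactions are handled the same way. No exposure adjustment is stated.
- **Window.** Section 11.4.5: "The analysis period will be from the initiation of study treatment to the examination at completion of study treatment or the examination at discontinuation". The footnote, printed under section 11.4.5.1, limits the second end point: "Subjects withdrawn from study participation". Serious events after the completion examination "will be tabulated separately, as necessary".
- **Collection off drug.** Section 6.13: "During study drug interruption and after study drug discontinuation, a survey to find whether any serious adverse events have occurred will be performed". The longest permitted interval between surveys is 8 weeks. The survey lists in sections 4.2.1.2 and 4.2.2.2 and in note n of Table 6-1 cover serious adverse events, efficacy events, bleeding events and selected drugs. Other non-serious events are not on them.
- **Conflicting collection text.** The first sentence of section 6.13, and section 9.4, read as if every adverse event is recorded up to the completion examination, on drug or off.
- **On-treatment window.** Section 11.4.2.1.2 defines one, "the study treatment period and up to 3 days after the last dose", with subjects at risk again when they resume drug. It is written for the efficacy sensitivity analysis only.

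**The concern.** A subject who stops drug early but stays in follow-up contributes two kinds of time to the same table. While on drug, all adverse events are recorded. Once off drug, non-serious, non-bleeding events are no longer asked about. The subject still counts once in the denominator.

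If off-drug time differs between arms, the arm with more of it shows fewer non-serious events for a reason unrelated to drug effect. Serious events are collected throughout, but those with onset long after last dose are counted together with on-drug events, which pulls a real on-drug difference towards the null.

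Unequal off-drug time is plausible, but its direction cannot be known in advance. Section 5.3.1 requires interruption when a prohibited drug such as an anticoagulant becomes necessary, and section 11.6 assumes twice the stroke and embolism hazard on placebo. In the other direction, section 9.1.2 anticipates interruption or discontinuation because of bleeding, which may be more frequent on DU-176b. The rule is therefore best fixed before unblinding.

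**Working it through.** No figure in the plan depends on this point, so there is none to reproduce. The check has a textual part and an illustration on assumed rates.

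**1. Who is in the window off drug.** Section 11.4.5 with its footnote moves the end forward only for subjects withdrawn from study participation. Under section 4.2.2.2, a subject who stops drug is surveyed until the completion examination. Such a subject therefore stays in the safety window with restricted adverse event collection.

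**2. Inputs for the illustration.**
- T = 2.5 years, the upper end of the planned mean treatment duration in section 5.2.1, used as the window length.
- Discontinuation hazard d: not in the documents. Assumed 0.10/year in one arm and 0.10, 0.15, 0.20 or 0.30/year in the other.
- True hazard h of a first non-serious, non-bleeding event: not in the documents. Assumed equal in both arms, at 0.05 to 1.0/year.
- Events are captured only before discontinuation. Discontinuation is permanent, and hazards are constant.

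**3. Captured crude incidence** = h/(h+d) × (1 − exp(−(h+d)T)).

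With h = 0.3:
- d = 0.10: 0.75 × (1 − exp(−1.00)) = 47.4%
- d = 0.20: 0.60 × (1 − exp(−1.25)) = 42.8%
- d = 0.30: 0.50 × (1 − exp(−1.50)) = 38.8%
- complete capture: 1 − exp(−0.75) = 52.8%

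Crude ratio, arm with more discontinuation over the other (true ratio 1.00):

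| d per year | h = 0.05 | h = 0.1 | h = 0.3 | h = 1.0 |
|---|---|---|---|---|
| 0.10 v 0.10 | 1.00 | 1.00 | 1.00 | 1.00 |
| 0.10 v 0.15 | 0.944 | 0.945 | 0.950 | 0.964 |
| 0.10 v 0.20 | 0.892 | 0.894 | 0.903 | 0.931 |
| 0.10 v 0.30 | 0.799 | 0.803 | 0.819 | 0.869 |

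With equal discontinuation both arms are under-counted (47.4% against 52.8% at h = 0.3), but the comparison is not distorted.

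**4. Which denominator corrects it.** On-treatment person-time to first event is (1 − exp(−(h+d)T))/(h+d). Dividing step 3 by this returns h exactly. At h = 0.3 that is 0.474/1.580 = 0.300 for d = 0.10 and 0.388/1.295 = 0.300 for d = 0.30, so the ratio is 1.00 in every scenario. Person-years over the full window do not work: for 0.10 v 0.30 the ratio is still 0.76 to 0.79. A last-dose cut-off with crude percentages does not work either, because in this model the captured events and the subject count are unchanged.

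**5. Dilution of serious events.** Suppose the on-drug ratio is 2.0, there is no effect off drug, events are rare, and f is the off-drug share of time in the DU-176b arm. The observed ratio is 2(1 − f) + f = 2 − f: 1.9 at f = 10% and 1.7 at f = 30%. The off-drug share implied by d is 1 − (1 − exp(−dT))/(dT): about 12%, 21% and 30% for d = 0.10, 0.20 and 0.30.

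**6. Stroke as the only cause of stopping.** If every primary event ended treatment, with 5%/year on placebo and 2.5%/year on DU-176b (section 11.6: 5%/year, hazard ratio 0.5), on-drug shares over 2.5 years would be (1 − exp(−0.125))/0.125 = 0.94 and (1 − exp(−0.0625))/0.0625 = 0.97. The ratio is about 1.03, so stroke alone is a small driver.

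**The case against.** - **The window does end.** A reader of section 11.4.5.2 alone might infer that treatment-emergent events have no end date. Section 11.4.5 supplies one. What stands is that this end is not anchored to last dose.
- **More than serious events are surveyed off drug.** A reader might infer from section 6.13 that only serious events are collected, and that major bleeding is compromised too. Sections 4.2.1.2, 4.2.2.2, 6.14 and 6.15 also require efficacy and bleeding events off drug, with no seriousness limit for bleeding. Section 11.4.5.1 analyses bleeding in the same way as the primary endpoint, which arguably brings in the on-treatment analysis. The ascertainment gap does not reach the primary safety endpoint.
- **The collection text can be read otherwise.** The first sentence of section 6.13, and section 9.4, taken alone, ask for all events to the completion examination. If sites followed that, the gap would be smaller. The explicit off-drug survey lists make the restricted reading likelier, and the conflict itself needs resolving.
- **A full-window serious event table is defensible.** It is the inclusive choice and should stay. The 3-day window is justified by half-life, and the discontinuation examination may fall up to 7 days after discontinuation (section 11.3.2), so events starting on days 4 to 7 would leave an on-treatment table. This argues for adding the split, not for dropping the full-window table.
- **Detail is deferred.** Section 11 refers to a separate statistical analysis plan, whose text is not in the document reviewed. It may already set a last-dose rule; this could not be checked. Such a rule would have to depart from the definition in section 11.4.5.2.

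**Conclusion.** The point holds for non-serious, non-bleeding adverse events, and as dilution for non-bleeding serious adverse events. As written, the tables combine two ascertainment regimes over one per-subject denominator.

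The size is unknown. On the assumed rates, the arm with more discontinuation looks safer by a crude ratio of 0.94 to 0.96 (0.10 v 0.15/year), 0.89 to 0.93 (0.10 v 0.20) or 0.80 to 0.87 (0.10 v 0.30), and there is no distortion if discontinuation is equal. A simple ratio of on-drug shares, such as 0.9/0.7 = 1.29, might suggest a larger effect. It holds only for rare events; inverting the 0.10 v 0.30 range gives 1.15 to 1.25. The documents do not support a claim that either arm in particular will be favoured.

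This is a cheap improvement to the safety tables. The primary efficacy analysis and the 65-event target are unaffected.

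**What to change.** 1. Report adverse events and adverse drug reactions as exposure-adjusted rates per on-treatment person-year, with the on-treatment window anchored to last dose. The plan's own window in section 11.4.2.1.2 is available, with interruptions handled as there. The dates needed are already collected (section 6.3).
2. Show serious adverse events with off-drug onset in a separate table, and keep the full-window serious event table as a complement.
3. Reconcile the first sentence of section 6.13, and section 9.4, with the off-drug survey lists in sections 4.2.1.2 and 4.2.2.2, so that it is clear which events are collected after drug is stopped or interrupted.

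Item 1 needs both parts: moving the cut-off to last dose while keeping crude percentages would not correct the non-serious comparison.

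The cost is analysis plan wording and one extra table set; no new data are needed. The downside is that events starting after the 3-day window, including some found at a discontinuation examination up to 7 days after stopping, appear in the off-drug table.

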11.4.5.3 Laboratory Data

Summary statistics for hematology and blood chemistry tests will be calculated by time point and by treatment group, and changes (time courses) before and after administration will be plotted. A shift table of assessment on normal and abnormal values will also be prepared. Frequencies of measured indicators from urinalysis (except for urinary sediment) will also be tabulated by time point and by treatment group.

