6.8 Laboratory Tests

Blood samples and urine samples for laboratory tests will be collected at the eligibility assessment examination, once every 8 weeks during the study treatment period (from Week 4 to Week 48, at Visit 3, Visit 5, Visit 7, Visit 9, Visit 11, and Visit 13/from Week 48 onward, at Visit 14, Visit 15, Visit 16...), the examination at completion of study

treatment, and the final follow-up examination or the examination at discontinuation. §§§
All laboratory tests will be performed as a batch by SRL, Inc.

- 1) Hematology test
 - Red blood cell count, hemoglobin, hematocrit, white blood cell count, white blood cell differentials (neutrophils, lymphocytes, monocytes, eosinophils, and basophils), platelet count, and PT-INR*
 - *: PT-INR will be measured if the subject received warfarin within the 8 weeks prior to the day of informed consent, or if the subject is receiving warfarin during study drug interruption or during the follow-up after study drug discontinuation.
- 2) Blood chemistry test
 - Total protein, albumin, total bilirubin, direct and indirect bilirubin, ** AST, ALT, ALP, GGT, LDH, CK, BUN, creatinine, uric acid, Na, K, Cl, total cholesterol, triglyceride **: Direct and indirect assays will be performed when total bilirubin ≥ 2 mg/dL
- Endocrinology tests
 Troponin I, human brain natriuretic peptide (BNP)
- 4) Urinalysis

Urine glucose, urine protein, urine blood, urinary sediment (red blood cells)

If the subject makes visits during study drug interruption or after study drug
discontinuation, measurement of laboratory test items the investigator or subinvestigator
considers suitable (if warfarin is being administered, PT-INR is mandatory) will be
requested, and the dates when specimens were collected will be entered on case report
forms.

If any abnormal laboratory data (deviations from reference ranges) are observed, the investigator or subinvestigator will assess whether to handle these data as an adverse event, and if they are considered to be adverse events, they will be entered in the adverse event field of the case report form.

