9.1.1 Major Bleeding

Overt bleeding that meets at least 1 of the following criteria will be taken to be major bleeding.

- Fatal bleeding
- Retroperitoneal, intracranial, intraocular, intrathecal, intraarticular, or periarticular bleeding, or symptomatic intramuscular bleeding accompanied by compartment syndrome
- Clinically overt bleeding that decreases hemoglobin by at least 2.0 g/dL and requires blood transfusion*
 - *: Transfusion of 1 unit of red cell concentrates or whole blood (about 200 mL) will be converted to a decrease in hemoglobin of 1.0 g/dL. For bleeding related to a surgical

^{†††††:} For subjects withdrawn from study participation

procedure, bleeding in excess of the usual quantity of bleeding for the surgery or procedure will be considered. If there are no data for hemoglobin, the criterion will be bleeding that decreases the hematocrit level by at least 6.0% and requires blood transfusion.

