9.1.3 Minor Bleeding

Other overt bleeding events that do not meet the criteria for major bleeding or clinically relevant non-major bleeding will be taken to be minor bleeding (for example, epistaxis that does not require treatment).

All events other than the above (such as a decrease in hemoglobin without overt bleeding) will all be classified as "no bleeding event."

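### The laboratory section has no per-subject count of large hemoglobin falls, so an arm difference in blood loss without overt bleeding may be diluted

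*Combined protocol and SAP*

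**What the plan says.** Section 11.4.5.3 (Laboratory Data) plans this for hematology: "Summary statistics for hematology and blood chemistry tests will be calculated by time point and by treatment group". It adds plots of change and a normal/abnormal table: "A shift table of assessment on normal and abnormal values will also be prepared". For urine it says: "Frequencies of measured indicators from urinalysis (except for urinary sediment) will also be tabulated by time point and by treatment group". Section 6.8 lists the urine items collected as "Urine glucose, urine protein, urine blood, urinary sediment (red blood cells"), so urine blood and sediment red cells are separate items and only the second is left out.

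Section 9.1.3 closes the bleeding classification with "All events other than the above (such as a decrease in hemoglobin without overt bleeding) will all be classified as" no bleeding event. The hemoglobin criterion for major bleeding in section 9.1.1 is "Clinically overt bleeding that decreases hemoglobin by at least 2.0 g/dL and requires blood transfusion".

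Section 6.8 schedules central laboratory tests every 8 weeks on treatment and at the completion, discontinuation and final follow-up examinations. Section 4.1.2 excludes patients with hemoglobin below 9 g/dL at the eligibility assessment.

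**The concern.** Bleeding is the primary safety question, in patients aged 80 or over who are enrolled because of bleeding risk. The Introduction says that major bleeding will be compared with placebo and its clinical acceptability judged. A hemoglobin fall without overt bleeding is outside all five bleeding analyses in section 11.4.5.1, whatever its size. It can appear only in the laboratory and adverse event tables.

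The planned laboratory displays are insensitive to this pattern. Visit-wise summaries spread a large fall in a few subjects over the whole arm. A two-category shift table does not move when an abnormal value becomes a worse abnormal value. If the arms differed in unexplained large falls, the safety judgment could be made without a table that shows it directly.

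**Working it through.** The documents contain no hemoglobin-fall figure to reproduce, so the core check is textual. The arithmetic is illustrative.

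**Text.**
- Sections 9.1.1 to 9.1.3: each category requires overt bleeding.
- Section 11.4.5.3: no threshold count, lowest value per subject or time to fall is planned.
- Shift table: entry is possible at 9 g/dL. The reference range is not given. If 9.5 g/dL lies below it, a fall from 9.5 to 7.0 g/dL is abnormal to abnormal and shows no shift.
- Off drug: between the discontinuation and completion examinations, section 6.8 leaves tests to the investigator's choice, and only if the subject visits. That interval is where the 8-weekly values stop.

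**Assumptions.** 400 per arm (section 11.6) and two-sided 5%. Falls of at least 2.0 g/dL, averaging 2.5 g/dL, occur in 10% on DU-176b and 5% on placebo. The SD of change is 1.0 to 1.3 g/dL. Only the 400 and the 2.0 g/dL come from the protocol.

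**Mean at one visit, every fall visible at it.**
- Difference = (0.10 − 0.05) × 2.5 = 0.125 g/dL.
- SE = SD × √(2/400) = 0.0707 (SD 1.0) or 0.0919 (SD 1.3).
- Power = Φ(0.125/SE − 1.96) = Φ(−0.19) = 42% or Φ(−0.60) = 27%.

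**Proportion of subjects.**
- Pooled SE = √(0.075 × 0.925 × 2/400) = 0.0186. Unpooled SE = √[(0.05 × 0.95 + 0.10 × 0.90)/400] = 0.0185.
- Power = Φ[(0.05 − 1.96 × 0.0186)/0.0185] = 77%.

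**Half the fallers unmeasured, in both analyses.**
- Mean: measured fallers are 20/380 and 10/390. The difference is (0.0526 − 0.0256) × 2.5 = 0.067 g/dL. With the same SEs, power is Φ(0.067/SE − 1.96) = 16% (SD 1.0) or 11% (SD 1.3).
- Proportion, unmeasured fallers counted as no fall (5% versus 2.5%): pooled SE 0.0134, unpooled SE 0.0134, power 46%. If they leave the denominator, power is 49%.

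**Short-lived falls.** Section 6.8 gives six hemoglobin visits to week 48, then one every 8 weeks: 6 + (104 − 48)/8 = 13 in 2 years. If each fall shows at only one of these, evenly spread, the mean difference per visit is 0.125/13 = about 0.01 g/dL.

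**The case against.** Several parts of the case against stand.

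- **Not only means.** The plan says summary statistics, which may include minima or quantiles. These still do not count subjects who fell from their own baseline.
- **Adverse events.** Section 9.2 includes abnormal laboratory findings and treats an aggravated concurrent condition as an adverse event, which covers the subject who is already anemic. Section 6.8 has the investigator assess each out-of-range value under blinding, and section 11.4.5.2 tabulates events by arm. A reader might therefore infer that the gap is closed. It is not: there is no numeric trigger, and section 6.13 narrows the off-drug survey to serious events.
- **Off-drug data.** A reader might infer that subjects who stop drug disappear from the hemoglobin data. The documents do not support that. Section 6.8 schedules tests at the discontinuation examination, and section 6.1 requires the completion examination for subjects who interrupted or discontinued treatment. Only the tests in between become discretionary.
- **Urine.** A reader might infer that urinary blood loss is dropped. Urine blood is still tabulated.
- **Power.** Setting 11–16% on the mean with missing fallers against 77% on the proportion without them would be unfair. Like for like, it is about 46% against 11–16%. The 10% versus 5% also describes all large falls, and those without overt bleeding would be a subset.
- **Background falls.** Ordinary variation adds falls in both arms. Under a normal distribution at one visit, Φ(−2.0/1.0) = 2.3% and Φ(−2.0/1.3) = 6.2% would pass 2.0 g/dL. The lowest of many values passes more often, so the background may exceed 5% and the count's advantage may be smaller than shown.
- **SAP.** Section 11 calls itself an overview and defers detail to a SAP. The supplied file has no separate SAP text, so the gap is shown for section 11 only.

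**Conclusion.** The point holds as a gap in safety reporting. As section 11.4.5.3 stands, a treatment difference in large hemoglobin falls without overt bleeding may be diluted in the laboratory displays, and the adverse event tables are only a discretionary backstop. The stronger conclusion, that such an excess would be hidden, is not supported, given the adverse event route, the scheduled examinations and the retained urine blood.

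The textual part needs no assumption. The size does: fall rates, fall size, SD and reference range are all assumed. Under those assumptions the per-subject proportion is clearly more sensitive than the visit mean, at 77% against 27–42%, or 46% against 11–16% with equal loss. These figures show direction and do not predict this trial's result.

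The primary efficacy test and the adjudicated bleeding endpoints as defined are untouched. This is a cheap improvement of minor to moderate importance.

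**What to change.** In section 11.4.5.3, or in the SAP before unblinding, add by treatment group:

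1. The number and percentage of subjects whose lowest post-baseline central hemoglobin is at least 2.0 g/dL below the eligibility value, with the difference and 95% CI. The threshold borrows only the size of fall in section 9.1.1, not its overt-bleeding and transfusion conditions.
2. How many of these subjects had no adjudicated bleeding event.
3. The number with any post-baseline value below 9 g/dL, the entry limit in section 4.1.2.
4. Sediment red cells alongside urine blood, by removing the sediment exception.

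Use all post-baseline central values, including those after interruption or discontinuation. State that the visit-window exclusion in section 11.3.2 does not apply to the lowest value. Report how many subjects in each arm have no post-baseline value.

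The bleeding definitions, visits and clinical procedures stay unchanged. The cost is SAP wording and a few tables from data already collected. The downside is that some falls will have causes other than bleeding, so the table should be labeled a supportive between-arm comparison and not a bleeding endpoint.
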